6.2. BASELINE

For this study, subjects will have 2 different baselines defined as follows:

- The first one (Baseline 1) will be the same as that defined in their previous study. This baseline was defined in the 029 as “baseline is defined as the last non-missing measurement taken prior to reference start date (including unscheduled assessments). In the case where the last non-missing measurement and the reference start date coincide, that measurement will be considered prior to baseline. However, AEs and medications commencing on the reference start date will be considered post baseline, unless the start time of the AE is known to be prior to the first dosing of the study medication.”
- The second one (Baseline 2) will be the intra-study baseline, defined as the last non-missing measurement prior to the first dose including pre-dose assessments performed on the reference start date. The intra-study baseline could correspond to:
 - Last assessment from the previous study (e.g. Day 11 for subjects from INS011-14-029)
 - Screening (Visit 1) assessment of INS011-14-030
 - Data collected at Day 1 (Visit 2) of INS011-14-030

Document: C:\Users\q832483\Documents\Insy CSR\Pending\Ready for QC\New folder\Statistical Analysis Plan.docx
Author: [REDACTED] Version Number: V1.0 Final
Version Date: 04APR2017

Template No: CS_TP_BS016 – Revision 3
Effective Date: 01May2012

Reference: CS_WI_BS005

6.3. RETESTS, UNSCHEDULED VISITS AND EARLY TERMINATION DATA

For by-visit summaries, data recorded at the nominal visit will be presented. Unscheduled measurements will not be included in by-visit summaries, but will contribute to the best/ worst case value where required (e.g. shift table).

In the case of a retest (same visit number assigned), the earliest available measurement for that visit will be used for by-visit summaries.

If the retest measurement occurs prior to the dosing of the first study medication, the retest measurement will be used in the summary statistics if it is the last measurement taken prior to the dose. The retest measurements will not be used in summary statistics for post dose measurements.

Early termination data will be mapped to the next available visit number for by-visit summaries.

Listings will include scheduled, unscheduled, retest and early discontinuation data.

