6.1.4 Clinical Laboratory Evaluations

All clinical laboratory tests will be reviewed for results of potential clinical significance throughout the study. The Investigator will evaluate any change in laboratory values. If the Investigator determines a laboratory abnormality to be clinically significant, it is considered a laboratory AE; however, if the abnormal laboratory value is consistent with a current diagnosis, it may be documented accordingly.

The following laboratory tests will be assessed at the time points specified by Table 1.

- Hematology: complete blood count (CBC) with differential, including platelet count, neutrophils, lymphocytes, eosinophils, basophils, monocytes, hemoglobin, and hematocrit
- Serum chemistry: total protein, albumin, creatinine, blood urea nitrogen (BUN), uric acid, total bilirubin, direct bilirubin, alkaline phosphatase, FSH, AST, ALT, glucose, calcium, phosphorus, bicarbonate, chloride, sodium, and potassium
- Urinalysis: specific gravity, pH, color, and presence of white blood cells (WBCs), red blood cells (RBCs), and proteins
- β -hCG in urine (pregnancy test)

LFTs (e.g., albumin, direct and total bilirubin, AST, and ALT) will be closely monitored to identify any damage that could be induced by the investigational product.

Levels of FSH will be monitored as a potential surrogate outcome for gametocyte damage.

Laboratory values outside the reference limits suspected to be of any clinical significance will be repeated. Subjects in whom suspected clinical significance is confirmed will either not be included or if already enrolled will be followed until normalization or for as long as the Investigator considers necessary. Additional laboratory variables may be performed for safety reasons if judged appropriate by the Investigator. Further details are provided in the Laboratory Manual.

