6.1.5.1 Vital Signs

Vital signs (including blood pressure, pulse rate, respiratory rate, and temperature) will be recorded at the time points specified by Table 1.

If clinically significant findings, as determined by the Investigator, occur in any of the vital signs measurements, that measurement will be repeated at medically appropriate intervals until the value returns to an acceptable range, a specific diagnosis is established, or the condition is otherwise explained.

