6.1.5.3 ECGs

The ECGs will be performed at the time points specified in Table 1.

Subjects should be supine for ≥ 5 minutes prior to the assessment.

If the first ECG is abnormal, up to an additional 2 repetitions of a specific assessment may be performed.

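### Retests prompted by an abnormal result can replace the first value at baseline but not after dosing, which tilts laboratory and qualitative ECG shift tables, and some mean changes, toward apparent worsening

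*SAP*

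**What the plan says.** SAP 6.3 sets two rules for retests. Before the first dose, "the retest measurement will be used in the summary statistics if it is the last measurement taken prior to the dose". After it, "The retest measurements will not be used in summary statistics for post dose measurements", and where a retest carries the same visit number "the earliest available measurement for that visit will be used for by-visit summaries". Unscheduled values stay out of by-visit summaries but "will contribute to the best/ worst case value where required (e.g. shift table").

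SAP 6.2 defines two baselines, and both take the last value before dosing. Baseline 1 is carried over from the previous study, where it was "the last non-missing measurement taken prior to reference start date (including unscheduled assessments"). Baseline 2 is the last non-missing value before the first dose of this study. A pre-dose retest can therefore become either baseline.

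The protocol ties repeats to the result:

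- ECG (Protocol 6.1.5.3, repeated in SAP 17.4): "If the first ECG is abnormal, up to an additional 2 repetitions of a specific assessment may be performed".
- Vital signs (Protocol 6.1.5.1): for a finding that the investigator judges clinically significant, "that measurement will be repeated at medically appropriate intervals until the value returns to an acceptable range", or until it is diagnosed or otherwise explained.
- Laboratory (Protocol 6.1.4): "Laboratory values outside the reference limits suspected to be of any clinical significance will be repeated".

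SAP 17.4 refers ECG retests to 6.3. SAP 17.3, 17.4 and 17.5 compare laboratory, ECG and vital-sign results with both baselines.

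**The concern.** A repeat taken because the first reading was abnormal will tend to be closer to normal, through regression to the mean alone. SAP 6.3 lets that correction operate at baseline and blocks it afterwards. With no drug effect, fewer subjects are abnormal at baseline than at follow-up.

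The study is open-label with no comparator, and changes from baseline in vital signs, ECG and laboratory values are named safety endpoints (Protocol 6.1.6). No control group would show the same artefact and expose it, and no planned sensitivity analysis applies one rule to both sides. Counting unscheduled values toward a worst case does not help, because a normal repeat cannot remove an abnormal first value from a worst-case display. Protocol 8.3.4.2, which counts each subject once at the worst grade in laboratory shift tables, pushes the same way.

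**Working it through.** The plan states no figure on this point, so there is nothing to reproduce. The check is a simulation with no drug effect.

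**Inputs from the documents.** Last pre-dose value at baseline (SAP 6.2, 6.3); first value after dosing (SAP 6.3); up to two ECG repeats (Protocol 6.1.5.3); at most 60 + 20 = 80 subjects (Protocol 8.1).

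**Assumed inputs, not in the documents.** 5% of first values abnormal, split between high and low; within-subject correlation 0.6; normally distributed values; the repeat rates shown below.

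**Model.** Value = subject effect + visit error, total SD 1, with the same distribution before and after dosing. An abnormal baseline value may be redrawn for the same subject. The follow-up value is never redrawn.

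| Rule | Normal to abnormal | Abnormal to normal |
|---|---|---|
| First value on both sides | 3.8% | 3.8% |
| SAP rule, half of abnormal values repeated once | 4.1% | 2.2% |
| SAP rule, every abnormal value repeated once | 4.5% | 0.7% |
| SAP rule, always up to two repeats | 4.7% | 0.2% |

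**Check by identity.** Normal-to-abnormal minus abnormal-to-normal equals the follow-up abnormal share minus the baseline abnormal share. Follow-up stays at 5.0%. The implied baseline shares for the three SAP rows are 5.0 − (4.1 − 2.2) = 3.1%, 5.0 − (4.5 − 0.7) = 1.2% and 5.0 − (4.7 − 0.2) = 0.5%. The imbalance comes wholly from the cleaned baseline.

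**In subjects, at N = 80.**

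- Extra normal-to-abnormal: 80 × (0.041 − 0.038) = 0.2, up to 80 × (0.047 − 0.038) = 0.7.
- Missing abnormal-to-normal: 80 × (0.038 − 0.022) = 1.3, up to 80 × (0.038 − 0.002) = 2.9.

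**Sensitivity to the assumed rate.** With 10% abnormal on one side only, correlation 0.7 and up to two repeats, shifts are 7.8% versus 0.8%, against 5.3% each way with first values on both sides. That is 80 × (0.078 − 0.053) = 2.0 extra subjects. With one repeat done half the time they are 6.2% versus 3.5%. Over one-sided scenarios with 5% to 20% abnormal, correlation 0.5 to 0.8 and up to two repeats, normal-to-abnormal runs from 3.7% to 16.7% and abnormal-to-normal from 0.2% to 1.7%.

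**Mean change.** It is 0.00 SD when high and low abnormality are symmetric. It is +0.03 to +0.18 SD over the one-sided scenarios with up to two repeats, and +0.03 SD at 10% abnormal, correlation 0.7, one repeat done half the time.

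**QTcF illustration** (assumed mean 405 ms, SD 14 between and 12 within subjects, up to two repeats). With a repeat above 430 ms, mean change is +1.5 ms, and rises over 30 ms go from 3.9% with first values on both sides to 4.3%. With a repeat only above 450 ms, the lowest absolute limit in SAP 17.4.1, mean change is about +0.2 ms and the over-30 ms share stays at 3.9%.

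**One rule on both sides.** First/first or last/last gives a mean change of 0.00 SD and balanced shifts.

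**The case against.** A reader might infer that the rule produces false worsening across all change and shift tables for ECG, vital signs and laboratory values alike. The planned outputs do not support that:

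- Vital signs have no shift table (SAP 17.5). Only change from baseline and the markedly abnormal criteria that include a change are exposed. The respiratory-rate criterion has no change component.
- ECG shifts cover qualitative results only, and the one scheduled post-dose ECG is at the Final/Discontinuation Visit (SAP 17.4; Protocol Table 1).
- Laboratory repeats need suspected clinical significance as well as an out-of-range value. Analysis is central (Protocol 6.1.4.1), so a Day 1 sample can seldom be retested before that day's dose.
- ECG repeats are optional, and assessments other than vital signs from the preceding 14 days may be reused for Visit 2 (Protocol 5.2.1), so some subjects will have no new pre-dose ECG or laboratory test.

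A reader might also take the ratio of the two shift directions (4.7% to 0.2%) as the size of a false harm signal. Most of it is missing recoveries. First values on both sides already give 3.8% normal-to-abnormal with an inert drug.

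Nor are the baseline comparisons the only safety evidence. ALT/AST above 3 × ULN, bilirubin above 2 × ULN, absolute QT/QTcF limits, adverse events and listings that include retests do not depend on baseline.

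Finally, keeping the first post-dose value tends to over-call harm, which can be defended as cautious in a descriptive study. That supports the post-dose rule on its own. It does not support pairing it with a different rule at baseline. All these limits stand, and they narrow the point without removing it.

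**Conclusion.** The asymmetry is explicit in SAP 6.2 and 6.3, and its direction follows from repeats being prompted by abnormal results. Shift tables are affected whether abnormality is one-sided or two-sided. Mean change is affected only where abnormality runs mainly one way.

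The size cannot be established from the documents. At 5% abnormal and correlation 0.6 it is under one extra normal-to-abnormal subject in 80 and roughly one to three missing abnormal-to-normal subjects. Higher abnormal rates would enlarge it; fewer repeats would shrink it. The effect is likely strongest for the ECG overall assessment, where repeats can be taken in the same pre-dose session, and weakest for laboratory tests.

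This is worth correcting because an uncontrolled study has no comparison to reveal the artefact. It does not invalidate the safety evaluation as a whole.

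**What to change.** Amend SAP 6.3 and the Baseline 2 definition in 6.2 so that change and shift tables use the same within-visit rule before and after dosing. For example, take the first valid value at the visit on both sides: for Baseline 2, choose the last pre-dose visit with data and use its first valid value. For ECG intervals the mean of the replicates on both sides would also serve. State that a repeat recorded as unscheduled is handled with the visit that prompted it.

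If the main tables are to stay as they are, at minimum add a first/first sensitivity table for ECG, vital-sign change, and laboratory and LFT shifts.

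For Baseline 1, apply the same rule where retest data from the previous study are available, and otherwise footnote the asymmetry. Changing 6.3 alone would leave Baseline 1 as it is. Keep retests in worst-case displays and listings.

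The cost is SAP wording, some extra derivation and tables, and a baseline that is not always the last value before the dose. No new data collection is needed.

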6.4. WINDOWING CONVENTIONS

For seizure data only, as the date only is collected on the Subject Diary - Seizure eCRF page, the time points will be assigned to each record considering the following visit windowing:

Table A: Study Day Windows

Assigned Study Day (Inclusive)		Target Day	Week Assigned
From	To		
-14	-1	N/A	Screening
1	1	1	Day 1
4	10	7	Week 1
11	17	14	Week 2
21	35	28	Week 4
49	63	56	Week 8
77	91	84	Week 12
158	178	168	Week 24
242	262	252	Week 36

For the final visit/discontinuation visit, the date should match with the last record from Seizure Diary eCRF page.

No other visit windowing of scheduled time points will be performed for this study. Data will be summarized based on the planned visit schedule.

Document: C:\Users\q832483\Documents\Insy CSR\Pending\Ready for QC\New folder\Statistical Analysis Plan.docx
Author: [REDACTED] Version Number: V1.0 Final
Version Date: 04APR2017

Template No: CS_TP_BS016 – Revision 3
Effective Date: 01May2012

Reference: CS_WI_BS005

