duration of treatment in INS011-14-030 will be based on the length of time they were enrolled in INS011-15-054 such that total duration of treatment in both studies combined will not exceed approximately 48 weeks. Subjects visit entry into INS011-14-030 will be determined at the discretion of the sponsor and the investigator.

The study will be terminated upon 1 of the following:

- The investigational product is successfully approved for marketing in the US
- Sponsor elects to terminate INS011-14-030.

Treatment with established background AEDs will continue without interruption and changes will be permitted as necessary based on safety concerns or due to changes in seizure control as described in Section 4.3.

As described in Table 1 and Section 5.0, visits will be scheduled at Week 1, Week 2, then monthly for 3 months, and then quarterly thereafter. A Screening Visit will be required for all subjects that do not rollover within 14 days of completing their previous study. All subjects will complete the Final Visit/ Discontinuation Visit regardless of when they stop treatment/complete the study. A Follow-up Visit will occur 2 weeks after the Final Visit/Discontinuation Visit.

At each visit, a record of the incidence and severity of adverse events (AEs), treatment-emergent AEs (TEAEs), and SAEs will be collected and this will serve as a primary outcome criterion for this study. Other safety-related parameters such as 12-lead ECG and hematology, chemistry, and urinary analyses will also be assessed at specified visits. Determination of trough plasma levels of cannabidiol and its 7-OH metabolite will be performed at each visit except Visits 3 and 4 (Week 1 and Week 2). This will support safety monitoring and establish the extent of variability during long-term treatment with the investigational product. For subjects taking clobazam, levels of clobazam and its major metabolite (norclobazam) will be measured if there are safety concerns. Seizure diaries will be reviewed to assess control of seizures (frequency, duration, and severity) throughout the duration of the study.

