5.2.5 Visits 8 and 9 (Quarterly Visits) ±10 days

Subjects will complete Visits 8 and 9 quarterly (every 3 months) at Weeks 24 and 36.

The following procedures will be completed:

- Record concomitant medications and concomitant procedures
- Record vital signs (blood pressure, heart rate, respiratory rate, and temperature measurements)

- Obtain a urine sample for serum β -hCG pregnancy test in female subjects of childbearing potential
- Draw blood samples for hematology and chemistry (fasting NOT required) and record whether subject was fasting at time of collection in the eCRF
- Obtain a urine sample for urinalysis
- Complete blood draw for plasma levels
- Perform physical examination (see Section 6.1.5.2), including height and weight
- Perform a brief neurology examination (see Section 6.1.5.2)
- Review subject seizure and dosing diary and collect completed pages
 - Re-education of the parent/caregiver and/or subject regarding diary completion will be conducted as needed in the opinion of the Investigator.
- Dispense new subject seizure and dosing diary
 - Diary data will be collected for one week (7 days) prior to the next visit.
- Administer morning dose of the investigational product in the clinic.
- Record recent medication history including current AEDs, vitamins, herbal preparations, blood products, and over-the-counter drugs
- Dispense and collect investigational product
- Review of dosing procedures for the investigational product
- Record AEs and SAEs
- Administer Investigator CGI-I and CGI-S
- Administer parent(s)/caregiver(s) CGI-I and CGI-S
 - When appropriate, subjects will complete the CGI-I and CGI-S for themselves.
- Administer IPES
 - The IPES is validated for subjects who are 2 to 16 years of (developmental) age. Due to developmental delay characteristic of the study population, subjects through 18 years of chronological age will complete the IPES.

- Administer C-SSRS (if appropriate)
- Remind subject/parent(s)/caregiver(s) of next scheduled visit. The subject/parent(s)/caregiver(s) should be reminded that the morning dose of the investigational product should not be administered prior to study assessments/clinic visit on the date of their next study visit and to record the date and time of the evening meal on the day prior to the next study visit.

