6.3 Efficacy

6.3.1 Seizure Control

In this study, seizure frequency, duration, and severity will be assessed to monitor seizure control achieved by long-term treatment with Cannabidiol Oral Solution. Seizures will be observed and recorded using a patient reported outcome (PRO) instrument (i.e.,

subject/caregiver diaries). The exact format and version(s) of diary to be used will also be included in the eCRF. Diaries will be dispensed at Visits 7, 8, and 9 (Weeks 12, 24, and 36) and reviewed and completed pages collected (if applicable) during each visit.

For the purposes of this study, only observable seizures will be quantified in the one week prior to Visits 8, 9, and 10. All seizures should be recorded by the parent(s)/caregiver(s) and/or subject (if applicable) in the diary.

Given that continuous seizures may be observed in some subjects (i.e., multiple seizures may occur without break), it may not be possible to accurately record all seizures for these subjects. If necessary, the parent(s)/caregiver(s) or subject (if applicable) will, at a minimum, categorize the seizure frequency (for seizures others than tonic or atonic seizures) by range (i.e., diaries will record the count of seizures per day as >50 seizures/day, 20 to 50 seizures/day, 6 to 19 seizures/day, 1 to 5 seizures/day, or no seizures).

The subject and/or his/her parent(s)/caregiver(s) are responsible for completing the diary. The party who is primarily responsible will be chosen by the Investigator in consultation with the subject's parent(s)/caregiver(s). If a pediatric subject will be entering diary data, the parent(s)/caregiver(s) should provide guidance and monitor accuracy and completeness.

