6. GENERAL CONSIDERATIONS

6.1. REFERENCE START DATE AND STUDY DAY

Study Day will be calculated from the reference start date, and will be used to show start/ stop day of assessments and events.

Reference start date is defined as the day of the first dose of study medication, (Day 1 is the day of the first dose of study medication), and will appear in every listing where an assessment date or event date appears.

- If the date of the event is on or after the reference date then:

Study Day = (date of event – reference date) + 1.

- If the date of the event is prior to the reference date then:

Study Day = (date of event – reference date).

In the situation where the event date is partial or missing, the date will appear partial or missing in the listings, and Study Day, and any corresponding durations will be presented based on the imputations specified in [Appendix 2](#); Partial Date Conventions.

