15.1. DERIVATIONS

Compliance to study medication will be based on the volume of medication and calculated as follows:

- "Per Visit" Compliance to study medication will be calculated as follows:

$$\frac{\text{Sum of administered volumes during the week before Visit X}}{\text{Sum of planned volumes during the week before Visit X}} \times 100$$

The compliance per visit will be summarized and reasons for which dose not administered will be listed. The compliance will be clustered as follows: <50%, [50%; 80%, [80%; 100%, [100%; 120%, >120%.

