16.2.1. SEIZURES-RELATED DATA

In this study, seizure frequency, duration, and severity will be assessed to monitor seizure control achieved by long-term treatment with Cannabidiol Oral Solution. Seizures will be observed and recorded using a patient reported outcome (PRO) instrument (i.e., subject/caregiver diaries). Seizures are collected at week 24, week 36 and final visit and they will be compared to the baseline from the previous study.

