16.2.1.1. Seizures-Related Variable(s) & Derivation(s)

The following variables will be used to assess the control of seizures:

- Type of seizures:
 - Tonic: body stiffening, upward deviation of the eyes, pupil dilation, and altered respiratory patterns
 - Atonic: brief loss of muscle tone and consciousness, that may result in an abrupt fall
 - Myoclonic: sudden muscle jerks and including infantile spasms
 - Tonic-clonic: jerking preceded by stiffening
 - Clonic: repeated jerking
 - Absence: lapses of awareness, sometimes with staring
 - Febrile: seizure of various types (especially tonic-clonic) associated with high fever
 - Focal: typically involving 1 side and/or region of the body, twitching, and grimacing
 - Atypical absence: staring (as in an absence seizure), but subject may also be somewhat responsive.
- Seizure frequency:

For tonic and atonic seizures, the number of seizures will be recorded. For other types of seizures, the frequency will be reported by range as follows:

- None
- 1 to 5 seizures
- 6 to 19 seizures
- 20 to 50 seizures

Document: C:\Users\q832483\Documents\Insys CSR\Pending\Ready for QC\New folder\Statistical Analysis Plan.docx
Author: [REDACTED] Version Number: V1.0 Final
Version Date: 04APR2017

Template No: CS_TP_BS016 – Revision 3
Effective Date: 01May2012

Reference: CS_WI_BS005

[REDACTED]

- > 50 seizures.
- Seizure severity:

The assessment of seizure severity will be recorded by the parent(s)/caregiver(s) in the subject seizure and dosing diary. Seizure severity will be categorized as:

- Mild
- Moderate
- Severe

Overall seizure severity will be captured using the CGI-S as described in [Section 16.2.2](#).

- Seizure duration:

The approximate timing of seizure will be recorded by the parent(s)/caregiver(s) in the subject seizure and dosing diary.

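### The seizure windows in SAP Table A are visit tolerances, but the diary covers the week before the visit, so planned diary days are dropped or may be given the wrong week

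*SAP*

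**What the plan says.** Table A in SAP 6.4 applies to seizure data only: "the time points will be assigned to each record considering the following visit windowing". Its rows include Week 24 (Days 158-178, target 168) and Week 36 (Days 242-262, target 252). The section allows no other windowing.

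The diary is defined in Protocol 6.3.1: "only observable seizures will be quantified in the one week prior to Visits 8, 9, and 10". The visit tolerance is in the heading of Protocol 5.2.5: "Visits 8 and 9 (Quarterly Visits) ±10 days". SAP 16.2.1.2 shows that the eCRF asks about seizures once per study day, so the records are daily.

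For dosing, taken from the same diary, SAP 15.1 uses a different anchor: "Sum of administered volumes during the week before Visit X".

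SAP 16.2.1 states "Seizures are collected at week 24, week 36 and final visit". Table A nevertheless has rows for Weeks 1 to 12 and none for Week 48. The final visit has a single sentence, which matches its date to the last diary record.

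On the origin of Study Day, SAP 6.1 says "Reference start date is defined as the day of the first dose of study medication". For INS011-15-054 subjects, Protocol 3.1 says "Subjects visit entry into INS011-14-030 will be determined at the discretion of the sponsor and the investigator".

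**The concern.** A window built for visit dates is applied to records that all precede the visit. If the visit falls near the lower limit of its tolerance, some or all of its diary lies before the window opens, although the subject and the site did what the protocol asks.

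Three further gaps add to this:

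- A subject who joins at a later visit has a smaller Study Day at Weeks 24 and 36 than Table A assumes.
- The final-visit sentence does not say how the other diary days of that week are assigned.
- SAP 16.2.1.3 does not say whether the number of tonic and atonic seizures is a weekly sum or a daily mean.

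With a weekly sum, a shortened week gives a lower post-baseline count at an unchanged seizure rate. A day whose question was left unanswered would also count as zero, although SAP 16.2.1.2 refuses to assume that such a day was seizure-free. The maximum-severity and maximum-frequency summaries can only fall or stay the same when days are lost. The net direction of change from baseline also depends on the length of the baseline diary, which the documents do not give.

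The seizure data are descriptive and are not formal endpoints, but they are the only diary evidence for the objective on continued seizure control.

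**Working it through.** **1. Reproducing Table A.** Window = 7 × week ± the protocol visit tolerance (±3 days for Weeks 1-2, ±7 for Weeks 4-12, ±10 for Weeks 24 and 36):

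- Week 1: 7 ± 3 = 4-10; Week 2: 14 ± 3 = 11-17
- Week 4: 28 ± 7 = 21-35; Week 8: 56 ± 7 = 49-63; Week 12: 84 ± 7 = 77-91
- Week 24: 168 ± 10 = 158-178; Week 36: 252 ± 10 = 242-262

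All seven rows match exactly, so these are visit windows.

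**2. Diary days kept.** For a visit on day V, the diary days are V−7 to V−1. For Week 24:

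| Visit relative to target | Visit day | Diary days | Kept of 7 |
|---|---|---|---|
| −10 | 158 | 151-157 | 0 |
| −9 | 159 | 152-158 | 1 |
| −8 | 160 | 153-159 | 2 |
| −7 | 161 | 154-160 | 3 |
| −6 | 162 | 155-161 | 4 |
| −5 | 163 | 156-162 | 5 |
| −4 | 164 | 157-163 | 6 |
| −3 to +10 | 165-178 | from 158-164 to 171-177 | 7 |

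Week 36 behaves identically for visits on Days 242-248. So 7 of the 21 permitted visit days lose data.

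**3. Share of diary days lost.** Actual visit timing is not in the documents, so it is assumed here and varied.

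- Uniform over ±10 days: (7+6+5+4+3+2+1) / (21 × 7) = 28/147 = 19.0%.
- Triangular, weight 11 − |d| for d days from target: lost = 7×1 + 6×2 + 5×3 + 4×4 + 3×5 + 2×6 + 1×7 = 84; total = 121 × 7 = 847; 84/847 = 9.9%.
- Normal, SD 3 days, truncated to ±10: 3.45%.

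Two day-count conventions could differ: the visit day might count as the last diary day, or Week 24 might be Day 169.

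| Visit timing | As above | Either convention changed | Both changed |
|---|---|---|---|
| Uniform | 19.0% | 21/147 = 14.3% | 16/147 = 10.9% |
| Triangular | 9.9% | 6.6% | 4.3% |
| Normal, SD 3 | 3.45% | 1.7% | 0.8% |

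**4. Effect on counts, uniform case.** One diary in 21 (5%) is wholly lost and so missing, which lowers n. The other 20 lose 21 of 20 × 7 = 140 days, or 15%. At a constant seizure rate the mean count falls 15% if it is a weekly sum and 0% if it is a daily mean.

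**5. Late entry from INS011-15-054.** SAP 6.2 lists the last assessment of the previous study as a possible baseline before first dose, which places that dose in the extension. With on-time visits, visit study day = 7 × (visit week − entry week). Entry weeks are not documented, so a range is shown.

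| Entry | Week 24 diary | Week 36 diary |
|---|---|---|
| Visit 2 | 161-167: Week 24 | 245-251: Week 36 |
| Week 1 | 154-160: 3 of 7 kept | 238-244: 3 of 7 kept |
| Week 2 | 147-153: no row | 231-237: no row |
| Week 4 | 133-139: no row | 217-223: no row |
| Week 8 | 105-111: no row | 189-195: no row |
| Week 12 | 77-83: labelled Week 12 | 161-167: labelled Week 24 |
| Week 24 | not applicable | 77-83: labelled Week 12 |

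**The case against.** The strongest reply accepts the mismatch and disputes its size.

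- **Visit timing.** Nothing suggests that visits spread evenly over ±10 days. Protocol 4.6 recommends a reminder call one week before each quarterly visit, which favours visits near target, where the loss is about 1-3%. This is fair, and the result should be read as a range.
- **Conventions.** If either day-count convention changes, 6 of 21 visit days lose data and no in-tolerance diary is wholly lost. That is correct. The figures of 7 and 1 in 21 follow the SAP's own target day and the plain sense of a diary kept before the visit.
- **Bias.** A lower count needs the weekly-sum reading. That is also correct, and the SAP does not settle it. SAP 16.2.1.2 covers unanswered days, not answered days outside a window, so the conflict with it concerns only the unanswered ones.
- **Late entry.** It affects at most 20 of 80 subjects, at unknown entry weeks, and the SAP does not state the Study Day origin expressly for them. Late visits can offset it: after Week 1 entry, a visit 10 days late keeps all 7 days. This part stays conditional.
- **Simpler remedy.** Extending the windows to Days 151-177 and 235-261 captures every in-tolerance diary of a Visit 2 entrant. It does not repair late entry: after entry at Week 12, the Week 36 diary (Days 161-167) would still be labelled Week 24.
- **Slipped visits.** Anchoring to the actual visit can drop planned days; a 3-day slip after recording has begun leaves 4 of 7. Scaling by answered days prevents this from lowering the count.
- **Importance.** Nothing is tested, no safety result is touched, and the listings keep every record. That limits the consequence but does not make the tables right.

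**Conclusion.** The concern holds. As written, SAP 6.4 removes correctly collected diary days from the Week 24 and Week 36 seizure summaries when a permitted visit is 4 to 10 days early. The nominal-visit approach of SAP 6.3 does not rescue them, because 6.4 makes an express exception for seizure data.

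The expected loss at each visit runs from about 1% to 19% of diary days, depending on visit timing and day-count convention. The mismatch itself is certain. The fall in counts rests on the weekly-sum reading, and the late-entry errors rest on Study Day restarting at the first extension dose and on entry after Visit 2. The point should be fixed, although it affects only descriptive summaries.

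**What to change.** Replace the post-baseline rows of Table A, for seizure data, with this rule: records dated 1 to 7 days before the actual date of Visit 8, Visit 9 or Visit 10/discontinuation belong to that visit and are labelled by nominal visit. This follows the protocol's diary definition and SAP 15.1, covers the final visit, and does not depend on the entry week. State how a discontinuation diary is labelled, given that SAP 6.3 maps early-termination data to the next available visit.

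For tonic and atonic seizures, report seizures per 7 answered days = 7 × total count / days with the seizure question answered. Put baseline on the same scale where the previous study's diary data allow, and show the number of answered days.

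For the remaining types, SAP 16.2.1.1 says "For other types of seizures, the frequency will be reported by range as follows". Keep that categorical summary and show the number of answered days beside it.

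The cost is SAP text and programming; no new data are needed.
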